12.3 Premature Trial Termination

Both the investigator (with regard to his/her participation) and the sponsor reserve the right to terminate the trial at any time. Should this become necessary, the procedures will be agreed upon after consultation between the two parties. In terminating the trial, the sponsor and the investigator will ensure that adequate consideration is given to the protection of the best interests of the subjects. Regulatory authorities and IECs/IRBs/REBs will be informed.

In addition, the sponsor reserves the right to terminate the participation of individual trial sites. Conditions that may warrant termination include, but are not limited to, insufficient adherence to protocol requirements and failure to enter subjects at an acceptable rate.

13 REPORTING AND PUBLICATION

13.1 Clinical Trial Report

The data and information collected during this trial will be reported in a clinical trial report prepared by the sponsor and submitted for comments and signature to the signatory investigators.

13.2 Confidentiality and Ownership of Trial Data

Any confidential information relating to the IMP or the trial, including any data and results from the trial will be the exclusive property of the sponsor. The investigator and any other persons involved in the trial will protect the confidentiality of this proprietary information belonging to the sponsor.

13.3 Publications and Public Disclosure

13.3.1 Publication Policy

At the end of the trial, one or more manuscripts for joint publication may be prepared in collaboration between the investigator(s) offered authorship and the sponsor. In a multi-site trial based on the collaboration of many sites, any publication of results must acknowledge all sites. Results from multi-site trials must be reported in entirety in a responsible and coherent manner and results from subsets should not be published in advance or without clear reference to the primary publication of the entire trial.

Authorship is granted based on the International Committee of Medical Journal Editors (ICMJE) criteria (see current official version: <http://www.icmje.org>). The total number of authors is based on the guideline from the relevant journal or congress. In the event of any disagreement in the content of a publication, both the investigator's and the sponsor's opinion will be fairly and sufficiently represented in the publication.

Any external CRO or laboratory involved in the conduct of this trial has no publication rights regarding this trial.

If the investigator wishes to independently publish/present any results from the trial, the draft manuscript/presentation must be submitted in writing to the sponsor for comments prior to submission. Comments will be given within 4 weeks from receipt of the draft manuscript. This statement does not give the sponsor any editorial rights over the content of a publication, other than to restrict the disclosure of the sponsor's intellectual property. If the matter considered for publication is deemed patentable by the sponsor, scientific publication will not be allowed until after a filed patent application is published. Under such conditions the publication will be modified or delayed at the investigator's discretion, to allow sufficient time for the sponsor to seek patent protection of the invention.

13.3.2 Public Disclosure Policy

ICMJE member journals have adopted a trials-registration policy as a condition for publication. This policy requires that all clinical trials be registered in a public, clinical trials registry. Thus, it is the responsibility of the sponsor to register the trial in an appropriate public registry, i.e. www.ClinicalTrials.gov; a website maintained by the National Library of Medicine (NLM) at the U.S. National Institutes of Health (NIH). The trial will also be made publicly available at the European Union (EU) Clinical Trials Register at www.clinicaltrialsregister.eu. Trial registration may occur in other registries in accordance with local regulatory requirements. A summary of the trial results is made publicly available in accordance with applicable regulatory requirements.

14 ETHICAL AND REGULATORY ASPECTS

14.1 Independent Ethics Committee / Institutional Review Board / Research Ethics Board

An IEC/IRB/REB will review the protocol and any amendments and advertisements used for recruitment. The IEC/IRB/REB will review the subject information sheet and the ICF, their updates (if any) and any written materials given to the subjects. A list of all IECs/IRBs/REBs to which the protocol has been submitted and the name of the committee chairmen will be included in the clinical trial report.

14.2 Regulatory Authorities Approval

The regulatory permission to perform the trial will be obtained in accordance with applicable regulatory requirements. All ethical and regulatory approvals must be available before a subject is exposed to any trial-related procedure, including screening tests for eligibility.

14.3 End-of-Trial and End-of-Trial Notification

The end of this trial is defined as the date of the last visit (Visit 8) of the last subject undergoing the trial. An end-of-trial declaration will be prepared when the trial has ended and will be submitted to the IECs/IRBs/REBs and regulatory authorities.

14.4 Ethical Conduct of the Trial

This trial will be conducted in accordance with the ethical principles that have their origins in the Declaration of Helsinki ([World Medical Association Declaration of Helsinki, 2013](#)), in compliance with the approved protocol, ICH-GCP and applicable regulatory requirements.

14.5 Subject Information and Consent

The investigator (or the person delegated by the investigator) will obtain a freely given written consent from each subject after an appropriate explanation of the aims, methods, sources of funding, any possible conflicts of interest, anticipated benefits, potential risks of the trial and the discomfort it may entail, post-trial provisions and any other aspects of the trial which are relevant to the subject's decision to participate. The trial subject must be given ample time to consider participation in the trial, before the consent is obtained. The Informed Consent Documents must be signed and dated by the subject and the investigator who has provided information to the subject regarding the trial before the subject is exposed to any trial-related procedure, including screening tests for eligibility. Subjects must be given the option of being informed about the general outcome and the results of the trial.

The investigator (or the person delegated by the investigator) will explain that the subject is completely free to refuse to enter the trial or to withdraw from it at any time, without any consequences for his/her further care and without the need to justify his/her decision.

The subject will receive a copy of the subject information and his/her signed ICF.

If new information becomes available that may be relevant to the trial subject's willingness to continue participation in the trial, a new subject information and ICF will be forwarded to the IECs/IRBs/REBs (and regulatory authorities, if required). The trial subjects will be informed about this new information and re-consent will be obtained.

Each subject will be informed that the monitor(s), quality assurance auditor(s) mandated by the sponsor, IRB/IEC/REB representatives or regulatory authority inspector(s), in accordance with applicable regulatory requirements, may review his/her source records and data. Data protection will be handled in compliance with national/local regulations.

14.6 Subject Participation Card

The subject will be provided with a Subject Participation Card bearing the following information:

- That he/she is participating in a clinical trial
- That he/she is treated with FE 201836 / Desmopressin / Placebo
- The name and phone number of the investigator
- The name, address and phone number of the sponsor

The subject will be asked to keep the Subject Participation Card in their possession at all times during the trial and to return it at the last trial visit, if applicable.

Each subject's primary care physician will be notified of their participation in the trial by the investigator, if the subject agrees and if applicable.

14.7 Compliance Reference Documents

The Declaration of Helsinki ([World Medical Association Declaration of Helsinki, 2013](#)), the consolidated ICH-GCP, the EU Clinical Trials Directive and other national laws in the countries where the trial takes place shall constitute the main reference guidelines for ethical and regulatory conduct.

15 LIABILITIES AND INSURANCE

15.1 ICH-GCP Responsibilities

The responsibilities of the sponsor, the monitor and the investigator are defined in the ICH-GCP consolidated guideline and applicable regulatory requirements in the countries where the trial takes place. The investigator is responsible for adhering to the ICH-GCP responsibilities of investigators, for dispensing the IMP in accordance with the approved protocol or an approved amendment and for its secure storage and safe handling throughout the trial.

15.2 Liabilities and Insurance

Ferring Pharmaceuticals A/S is, as sponsor, responsible for ensuring appropriate general/product liability insurance and, as required in accordance with applicable laws and regulations, country-specific liability insurance coverage for claims made by a trial subject for injury arising from the subject's participation in the trial.

16 ARCHIVING

16.1 Investigator File

The investigator is responsible for maintaining all the records, which enable the conduct of the trial at the site to be fully understood, in compliance with ICH-GCP. The trial documentation including all the relevant correspondence should be kept by the investigator for at least 15 years after the completion or discontinuation of the trial, if no further instructions are given by the sponsor.

The investigator is responsible for the completion and maintenance of the confidential subject identification code which provides the sole link between named subject source records and anonymous eCRF data for the sponsor. The investigator must arrange for the retention of this subject identification log and signed informed consent documents for at least 15 years after the completion or discontinuation of the trial.

No trial site document may be destroyed without prior written agreement between the investigator and the sponsor. Should the investigator elect to assign the trial documents to another party, or move them to another location, the sponsor must be notified in advance. If the investigator retires and the documents can no longer be archived by the site, the sponsor can arrange having the Investigator File archived at an external archive.

16.2 Trial Master File

The sponsor will archive the Trial Master File in accordance with ICH-GCP and applicable regulatory requirements.

Ferring Pharmaceuticals is developing FE201836, which is designed to act as a V_2 agonist with an antidiuretic action for the intention to treat nocturia due to nocturnal polyuria in adults. In addition to the frequency of nocturia as a primary endpoint, Ferring wishes to use the Nocturia Impact (NI) Diary as a co-primary endpoint in its registrational studies. The NI Diary is a 12-item, unidimensional 3-day diary of the impact associated with nocturia. As part of the measure validation, the Food and Drug Administration (FDA) Division of Bone, Reproductive, and Urologic Products has requested that subjects are interviewed as they exit the trial to help with understanding what subjects believe is a meaningful change in score. More recently, the FDA have asked that subjects within this study also be asked what constitutes a meaningful reduction in nocturnal voids. This protocol synopsis outlines the study design, sampling characteristics, and methodology for how the exit interviews will be conducted and provides the discussion guide for use with the subjects.

2 Objectives

This is an exit interview study, which will focus on data collection from subjects participating in an ongoing Phase 2 clinical trial of primarily adults in the United States (US) who have nocturia. The main objectives of this study are as follows:

1. Collection of qualitative feedback about the impact of nocturia on a subject's quality of life
2. Assessment of the subject's perception of what constitutes a clinically meaningful change on the NI Diary ([Appendix A](#))
3. Determination of what reduction in nocturnal voids is meaningful to patients ([Appendix B](#))
4. Map the exit interviews back to the clinical trial data to interpret the clinical endpoints

3 Study Methodology

This study is designed to examine the impact of living with nocturia and to assess what a meaningful positive change would be from the patient's perspective in terms of this impact. In exit interviews, patients' ratings and perceptions of changes will be collected using qualitative and quantitative methods. These data will be used to aid in understanding what is (from the perspective of patients) a meaningful change threshold for indicating positive improvement in the impact of nocturia on a patient's life and, also, meaningful change in nocturnal voids.

This study will include an initial sample of 66 English speaking patients who have been enrolled in a Phase 2 proof of concept FE201836 trial: "A Randomised, Double-blind, Placebo-controlled, Response-adaptive, Dose-finding Trial Investigating the Efficacy, Safety and Tolerability of Oral Doses of FE 201836, with Desmopressin Orally Disintegrating Tablet as a Benchmark, During 12 Weeks of Treatment for Nocturia due to Nocturnal Polyuria in Adults"

To ensure the generalizability of exit interview results, participants will be sampled based on a hierarchical cluster design. Included patients will be proportionate to the clinical trial sample distribution with respect to demographic and clinical characteristics (see Section 4.2 for further details).⁴

Of note: No tests will be conducted as a direct result of this study. No additional visits to a clinical facility will be necessary as part of this study. No identifying information of the patients will be retained by the research team.

4 Study Procedures

4.1 Study Overview

Subjects will be interviewed by telephone within 2-weeks of exiting the trial; those who withdraw early will not be interviewed. Clinical Outcomes Solutions will monitor all subject recruitment via weekly update reports from Quintiles to allow for arrangement with sites to conduct the exit interviews with subjects as they are finishing the trial.

4.2 Sample Size Requirement and Cluster Sampling Design

The primary goal of the exit interview is to estimate meaningful change thresholds for the NI diary within this randomized subject population from the Phase 2 proof-of-concept trial (1:1:1:1:1 ratio; FE201836 versus desmopressin versus placebo). For each treatment arm, subjects who demonstrate improvement in the NI Diary scores from Baseline to End of Treatment will be evaluated using a paired-sample t-test. This sample size calculation is based on NI diary parameters and is a mixed methods design (eg, qualitative and quantitative evidence) in which the equivalence of paired means is tested with significance (alpha) set at 0.05, a correlation of 0.40 between assessments, a combined standard deviation of 10 (95% confidence interval [CI] lower bound equal to 10 and upper bound equal to 15), and minimal difference thresholds estimated from previous research of 8.28 and 10.30 point improvement (based on the 0 – 100 transformation). See [Table 1](#) for further details.

Table 1. Sample Size Requirement for Paired t-test of Mean Difference

Mean Improvement Level on the NI Diary Total	Standard Deviation	Actual Power	Sample Requirement per Treatment Arm	Total Subjects
8.28	10	0.807	16 subjects	96 subjects
10.30	10	0.802	11 subjects	66 subjects

Abbreviations: NI = Nocturia Impact

The above power calculation defines the size of the initial set of exit interviews and the *minimum number of subjects* who will be exit interviewed. On the basis of this sample, the change threshold is estimated for defining meaningful change. Next, the robustness of the threshold estimate to increases in sample size using the steps described below is tested). Based on the results, it will be decided whether or not to conduct additional interviews. A “robust” threshold estimate is defined as one that varies < 1 with the addition of the results of additional interviews.

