4.2.1 Interview Steps Delineated

- Conduct the initial 66 exit interviews and estimate the threshold for meaningful change based on results for subjects indicating any level of improvement on the NI Diary Total Score.
- Calculate the mean, standard deviation (SD), and 95% CI of the change threshold estimate based on the initial sample size of 66 subjects. If variability in the estimate is greater than the population 10-point standard deviation, an additional 5% of subjects (or 1 subject per treatment arm) will be

interviewed. The threshold will be recalculated to determine if the estimate becomes robust enough to discontinue sampling when the estimate (in whole units) does not change with 2 successive sample size increases (eg, measurement saturation).

- If measurement saturation has been reached, exit interviews will be complete. If not, subjects will continue to be interviewed at an increase of 5% of subjects per treatment arm until measurement saturation is reached.

Please see [Table 2](#) for further details.

Table 2. Cluster Sampling Design Description

Cluster	Listing Unit	Elementary Unit	Application	Methodology for Exit Interviews
Baseline severity (nocturnal voids ≥ 2)	Sites (US and Europe)	Subject: 
 • Sex (50% female) • Age (50% ≥ 65) 	
 • Inclusion of proportionate number of subjects with nocturnal voids ≥ 2 to derive meaningful change thresholds 	
 • Start with 66 subjects and increase the proportion stepwise until measurement saturation is achieved • Measurement saturation will be defined by narrowing of the 95% CIs and an effect size above 0.50 (moderate)

Abbreviations: CI, confidence interval; NI, Nocturia Impact; US, United States

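### The exit-interview t-test and threshold estimate keep only subjects whose NI Diary score improved, so the test does not hold its 5% level and any threshold taken from observed change is biased upward

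*Protocol*

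**What the plan says.** Appendix 1, Section 4.2, gives estimation of meaningful change thresholds for the NI Diary as the primary goal of the exit interviews. It plans a test within each arm in which "subjects who demonstrate improvement in the NI Diary scores from Baseline to End of Treatment will be evaluated using a paired-sample t-test". Section 4.2.1 then has the threshold estimated from the first 66 interviews "based on results for subjects indicating any level of improvement on the NI Diary Total Score".

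The sample size in Section 4.2 rests on these inputs:

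- Significance level of the paired test: 0.05.
- Correlation of the two measurements: 0.40.
- Spread of the scores: "a combined standard deviation of 10 (95% confidence interval [CI] lower bound equal to 10 and upper bound equal to 15".
- Planning thresholds, taken from earlier work: improvements of 8.28 and 10.30 points on the 0 to 100 scale.

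Table 1 gives 16 subjects per arm (power 0.807, total 96) for 8.28 points and 11 per arm (power 0.802, total 66) for 10.30 points. The second row is the one adopted; Section 3 says "This study will include an initial sample of 66 English speaking patients". Section 4.2 presents these numbers as the minimum to be interviewed, not as a number of improvers.

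Section 1 explains why the threshold matters: the sponsor wants to use the NI Diary "as a co-primary endpoint in its registrational studies", and the regulator asked for the interviews.

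**The concern.** A subject enters these two steps only if his or her own change score lies in the favourable direction, and that same score is then tested or used for estimation. If nobody truly changes, about half will still improve by chance. Their mean change is positive by construction, so a test of zero mean change in that group says almost nothing about treatment or about meaningful change.

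The sample size calculation makes no such selection, so the analysis described is not the one that was powered. What is at stake is the credibility of a threshold meant to support interpretation of the NI Diary in later trials. If it draws on improvers' observed changes, it will be too high.

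**Working it through.** **Reproducing Table 1.** With SD 10 at each assessment and correlation 0.40, the SD of change is √(10² + 10² − 2 × 0.40 × 10 × 10) = √120 = 10.954. A two-sided paired t-test at 0.05 (noncentral t) gives:

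| Mean change | n per arm | Power recomputed | Power in Table 1 |
|---|---|---|---|
| 8.28 | 16 | 0.8066 | 0.807 |
| 10.30 | 11 | 0.8021 | 0.802 |

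Both rows reproduce with unselected changes. The variants tried do not reproduce them: a one-sided test gives 13 and 9, an SD of change of 10 gives 14 and 10, and a normal approximation gives 14 and 9. The plan does not state sidedness, so two-sided is inferred from this match.

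**Mean change among improvers when nothing changes.** Let D be the change, scored so that improvement is positive, with D ~ N(0, 10.954²). Then E[D | D > 0] = 10.954 × √(2/π) = 10.954 × 0.7979 = 8.74 points. This is 0.46 above 8.28 and 1.56 below 10.30.

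Sensitivity:

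- SD 15, the stated upper bound: SD of change 16.43, improvers' mean 13.1, above both thresholds.
- SD of change 10 (a reading that does not reproduce Table 1): improvers' mean 7.98, below both.
- At correlation 0.40, the noise-only mean passes 10.30 only if the SD exceeds 10.30 / (0.7979 × 1.0954) ≈ 11.8.

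Pooling the improvers among 66 interviewees, their mean exceeds 8.28 in 65% of simulated samples and 10.30 in 9%.

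**Rejection rate of the t-test under zero true change** (200,000 simulated samples, two-sided 5% critical value, SD 10):

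| Who is analysed, per arm | Rejection rate |
|---|---|
| Improvers among 11 interviewed (about 5.5 on average) | 69% |
| Improvers among 16 interviewed (about 8 on average) | 92% |
| Exactly 11 improvers | 99.96% |
| Exactly 16 improvers | about 100% |
| All 11 interviewed, no selection | 5.0% |
| All 16 interviewed, no selection | 4.9% |

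The first two rows match the plan's statement that the numbers are interviews. The rates at SD 15 are essentially the same, because the t statistic does not depend on scale.

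**Bias when there is a true change.** With true mean 8.28, a = 8.28 / 10.954 = 0.756, and E[D | D > 0] = 8.28 + 10.954 × φ(a)/Φ(a) = 8.28 + 4.24 = 12.5 points. Selection adds about 4.2 points.

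**The case against.** The strongest reply is that the documents never define the threshold as the improvers' mean observed change. The discussion guide (Appendix 1, Appendix D, Questions 8 to 11) asks subjects which impacts must improve and how many points on each would be meaningful, then sums the answers and checks the total with the subject. A half-normal mean of change scores is not the bias of a figure obtained that way. This stands. A reader might infer that the final threshold would be pure noise; the documents do not support that. They also do not say how stated points and observed change are to be combined, so the bias applies only to the part resting on observed change.

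A reader might also infer that subjects who stayed the same or worsened are lost to the study. They are not. Section 3 samples interviewees in proportion to the trial population, Questions 8 to 11 are open to all, and Section 5.3 compares subjects who feel better with those who feel worse and stratifies by PGI-I response. Anchor analyses with PGI-I and PGI-S are already planned in protocol Sections 7.1.1.3.1 and 10.3.1.1, with details in a separate psychometric plan that is not among the documents reviewed. The restriction to improvers is confined to the t-test and the threshold step.

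Two numerical readings also go too far. Noise alone does not clear both planning thresholds at the stated SD of 10: 8.74 lies below the 10.30 behind the 66-subject sample. Nor is rejection near certain at the planned number of interviews; that needs 11 or 16 improvers per arm, and under no change 11 improvers would take about 22 interviews.

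Finally, no stated decision depends on the t-test, and interest in positive improvement partly explains looking at improvers. Both are fair and limit the consequence. Neither makes a test conditioned on the sign of its own outcome valid.

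**Conclusion.** The point holds for the paired t-test in Section 4.2 and the threshold step in Section 4.2.1. Both select on the outcome, and the test as written does not match the calculation behind Table 1. Its false-positive rate is about 69% with 11 interviewed per arm and 92% with 16, instead of 5%. Observed change among improvers is inflated to 8.74 points when the truth is zero and to about 12.5 when the truth is 8.28.

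These figures assume normally distributed changes, the plan's SD of 10 and correlation of 0.40, and a two-sided test. The noise-only mean ranges from 7.98 to 13.1 over the SD readings shown. How far the threshold itself is biased cannot be quantified, because its estimator is not specified. The matter should be corrected, but it is confined to the exit-interview study and does not touch the trial's primary dose-response analysis.

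**What to change.** In Appendix 1, delete the restriction to improvers in Sections 4.2 and 4.2.1. Run the paired test on all interviewed completers in each arm, the population for which the 16 and 11 in Table 1 are valid, or drop the test.

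If a threshold specific to improvement is wanted, define improvement by an anchor other than the NI Diary score. PGI-I and PGI-S are already collected; one example is NI Diary change in subjects who report being a little better against those who report no change. This agrees with the anchor analyses already planned. Add a sentence stating how the points given in the interview and the observed change scores together produce the threshold.

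The cost is a wording change and a small change to the analysis. No new data are needed, and the planned number of interviews need not change on this account.
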